10.2. Patient Disposition

All patient discontinuations will be documented, and the extent of each patient's participation in the study will be reported. If known, a reason for their discontinuation will be given.

Discontinuations due to AE or death will be listed and summarized with cause of death further partitioned into AE, study disease, or other cause and summarized.

10.3. Patient Characteristics

Patient characteristics will include a summary of the following:

- Patient demographics including age, sex, and screening height and weight
- Baseline disease characteristics
- Prior disease-related therapies
- Concomitant medications.

Other patient characteristics will be summarized as deemed appropriate.

10.4. Safety Analyses

All patients who have been exposed to LY3164530 will be evaluated for safety and toxicity. Adverse event terms and severity grades will be assigned by the investigator using CTCAE v 4.03.

Safety analyses will include summaries of the following:

- AEs, including severity and possible relationship to study drug
- dose adjustments (reductions, omissions, and delays)
- laboratory values
- vital signs
- DLTs at each dose level
- ECGs
- Extent of concomitant medications.

10.5. Pharmacokinetic Analyses

Pharmacokinetic analyses will be conducted on patients who have been exposed to study drug and have had samples collected.

Pharmacokinetic parameter estimates for LY3164530 will be calculated by standard noncompartmental methods of analysis.

The primary parameters for analysis will be C_{max} , $AUC_{0-t_{last}}$, $AUC_{0-\tau}$, and $AUC_{0-\infty}$ of LY3164530. Other noncompartmental parameters, such as $t_{1/2}$, CL, volume of distribution (V), and accumulation ratios may be reported. Additional exploratory analyses will be performed if warranted by the data, and other validated PK software programs may be used if appropriate and approved by Lilly Global PK/PD management. The version of any software used for the analysis will be documented and the program will meet the Lilly requirements of software validation.

Pharmacokinetic parameter estimates will be evaluated to delineate effects of dose proportionality and temporal linearity. Log-transformed C_{max} and AUC estimates will be assessed to estimate ratios of geometric means and the corresponding 90% confidence intervals (CIs).

10.6. Pharmacodynamic Analyses

Provided that the data allows, PD and immunogenicity data from all patients may be analyzed using linear and/or nonlinear fixed and mixed effects models as appropriate. Pharmacodynamic and immunogenicity data will be summarized by dose, drug concentrations, and time from dose for each schedule of administration. Potential PD markers and immunogenicity versus time data will be presented graphically for each patient and summarized by dose and schedule of administration. Absolute and/or percent change from baseline for the PD markers may also be evaluated. Data may be log-transformed prior to summarizing if necessary. The interpatient and inpatient variability of the PD markers and immunogenicity responses may also be assessed where appropriate. Baseline measurements may be evaluated as potential covariates to assess their relationship to relevant PD responses.

10.7. Pharmacokinetic/Pharmacodynamic Analyses

In addition to a standard noncompartmental assessment, and provided that the data allows, the LY3164530 serum concentration-time data may be evaluated by model-based approaches as

warranted. Additional analyses, such as exposure-response modeling using the efficacy endpoints, may also be explored.

Additional exploratory analyses may be performed if warranted by the data.

10.8. Efficacy

The study was not designed to make an efficacy assessment. However, any tumor response data and duration of treatment will be tabulated.

10.9. Biomarker Analyses

Biomarker assessments in this study will focus on identifying markers and/or marker signatures that may indicate the patients most likely to respond or be resistant to LY3164530.

In archived and pre-treatment tissue samples, biomarker data related to the MET and EGFR pathways and cancer pathobiology may be analyzed to assess any potential correlation with response to LY3164530. These analyses may include, but are not limited to, MET and EGFR protein expression, circulating DNA, somatic mutation status, and/or copy number variations of MET and EGFR pathway-related genes (eg, KRAS, BRAF) or genes related to cancer pathobiology. In addition, tumor sample based gene signature(s) may be defined and evaluated to explore whether they are associated with response to LY3164530. In all analyses, adjustments may be made to account for other baseline patient characteristics, safety, and PK/PD data.

Unless otherwise stated, given the small sample sizes involved, statistical analyses results will be considered exploratory and will not consider multiple comparison adjustments.

10.10. Interim Analyses

Since this is a dose-escalation study, data will be reviewed on an ongoing basis during the study until the RP2D is determined. The purpose of these ongoing reviews is to evaluate the safety data at each dose level. A review of the data will be completed approximately after 6 patients have been treated for at least 1 cycle at a dose level without a cohort analysis.

An interim analysis will be triggered when at least 15 patients have been dosed at a given dose level for 1 cycle of treatment to evaluate the safety and tolerability of LY3164530. The interim analysis may include, but are not limited to, an assessment of available safety, PK, and PD data.

Enrollment may continue during the interim analysis and the dose escalation rules as outlined in [Figure JNBA.1](#) will continue to be followed.

Additional interim analyses may be triggered and may include, but are not limited to, assessment of available safety, PK, and PD data.

11. Informed Consent, Ethical Review, and Regulatory Considerations

11.1. Informed Consent

The investigator is responsible for ensuring that the patient understands the potential risks and benefits of participating in the study, including answering any questions the patient may have throughout the study and sharing in a timely manner any new information that may be relevant to the patient's willingness to continue his or her participation in the study in a timely manner.

The ICF will be used to explain the potential risks and benefits of study participation to the patient in simple terms before the patient is entered into the study and to document that the patient is satisfied with his or her understanding of the potential risks and benefits of participating in the study and desires to participate in the study.

The investigator is ultimately responsible for ensuring that informed consent is given by each patient before the study is started. This includes obtaining the appropriate signatures and dates on the ICF prior to the performance of any protocol procedures and prior to the administration of study drug.

In this protocol, the term "informed consent" includes all consent given by patients or their legal representatives.

11.2. Ethical Review

Lilly or its representatives must approve all ICFs before they are used at investigative sites(s). All ICFs must be compliant with the ICH guideline on GCP.

Documentation of ERB approval of the protocol and the ICF must be provided to Lilly before the study may begin at the investigative site(s). The ERB(s) will review the protocol as required.

The study site's ERB(s) should be provided with the following:

- the current Investigator's Brochure and updates during the course of the study
- ICF
- relevant curricula vitae.

11.3. Regulatory Considerations

This study will be conducted in accordance with:

- 1) consensus ethics principles derived from international ethics guidelines, including the Declaration of Helsinki and Council for International Organizations of Medical Sciences (CIOMS) International Ethical Guidelines
- 2) the ICH GCP Guideline [E6]
- 3) applicable laws and regulations.

The investigator or designee will promptly submit the protocol to applicable ERB(s).

An identification code assigned by the investigator to each patient will be used in lieu of the patient's name to protect the patient's identity when reporting AEs and/or other study-related data.

11.3.1. Investigator Information

Site-specific contact information may be provided in a separate document.

11.3.2. Protocol Signatures

The Sponsor's responsible medical officer will approve the protocol, confirming that, to the best of his or her knowledge, the protocol accurately describes the planned design and conduct of the study.

After reading the protocol, each principal investigator will sign the protocol signature page and send a copy of the signed page to a Lilly representative.

Attachment 1. Protocol JNBA Study Schedule

Baseline Schedule

Study Period	Baseline	
Cycle	BL	
Visit	0	
Duration	Up to 28 days	
Relative Day to C1D1	≤28	≤14

Procedure Category	Procedure			Comments
Study Entry/ Enrollment	Informed consent form signed (prior to conducting any protocol-specific tests/procedures)	X		
	Inclusion/Exclusion evaluation		X	
Medical History	Initial history/preexisting conditions		X	
	Historical illnesses		X	Include HPV status if known in tumor as part of historical assessment and denote on eCRF.
Physical Examination	Physical examination (including height and weight)		X	
	ECOG performance status		X	
	Vital signs		X	Includes blood pressure, pulse, and temperature.
Tumor Assessment	Radiologic imaging according to RECIST 1.1	X		Radiologic assessments obtained previously as part of routine clinical care may be used as the baseline assessment. This may be CT scan or MRI.
	Tumor measurement (palpable or visible)		X	
Adverse Events Collection/CTCAE Grading		X		
Concomitant Medication Notation		X		

Baseline Schedule

Study Period	Baseline		
Cycle	BL		
Visit	0		
Duration	Up to 28 days		
Relative Day to C1D1	≤28	≤14	≤7

Procedure Category	Procedure				Comments
Lab/ Diagnostic Tests	Local hematology		X		
	Local chemistry		X		
	Local coagulation		X		
	Local urinalysis		X		
	Local pregnancy test			X	Must be done ≤7 days prior to the first dose of study drug if patient is a woman of child-bearing potential. May be urine or serum specimen.
	Central ECG		X		Triplicate ECG.
	Biopsy of pretreatment tumor tissue		X		Unless the Sponsor and investigator document that the biopsy may be omitted; sample should be taken only after study eligibility is confirmed
	Archived tumor tissue (only if available)		X		Only for those patients that meet inclusion/exclusion criteria
	Tumor markers		X		Only if appropriate for the tumor type of the patient.
	Exploratory biomarker blood sample		X		If possible, this sample should be collected on the same day as the biopsy.
	Immunogenicity sample		X		

During Treatment Study Schedule

		Study Period	Study Treatment Period															
		Cycle/Visit	1				2				3-X ^a							
		Duration	28 days				28 days				28 days							
		Relative Day within Dosing Cycle	1	2	3	8	15	22	1	8	15	22	1	8	15	22		
Procedure Category	Procedure															Comments		
Physical Examination	Physical exam (including weight and skin inspections)	X						X				X				May be completed up to 7 days prior to the treatment infusion.		
	Vital signs	X			X	X	X	X	X	X	X	X	X*	X	X*	Includes blood pressure, pulse, and temperature. For Cycles 1-2, at a minimum, vital signs should be obtained prior to infusion, during infusion, and at 1 hour EOI (Section 7.2.4.1). In Cycle 3-X, vital signs should be taken predose and when clinically indicated. * Only need to be collected for patients on Schedule 2		
	ECOG performance status	X						X				X				May be completed up to 7 days prior to the treatment infusion		
Lab/Diagnostic Tests	Local hematology	X	X	X	X	X	X	X	X	X	X	X		X		. May be drawn up to 1 day prior to the planned assessment. On C1D1, post-dose samples should be drawn. See Attachment 4 Schedule 2: In Cycle 3-X, if clinically significant changes are observed, hematology should be obtained at least weekly until no longer clinically significant.		
	Local chemistry	X	X	X	X	X	X	X	X	X	X	X		X		May be drawn up to 1 day prior to the planned assessment. On C1D1, post-dose samples should be drawn. See Attachment 4 . Schedule 2: In Cycle 3-X, if clinically significant changes are observed, chemistry should be obtained at least weekly until no longer clinically significant.		
	Local Urinalysis	X						X				X				May be assessed up to 3 days prior to the planned assessment.		
	PK sampling		X						X					X				See Attachment 3 .
	Immunogenicity Sample	X						X				X				In addition to the scheduled samples, if a patient should have an infusion-related reaction to LY3164530, all attempts should be made to obtain immunogenicity sample as close to the onset of the event as possible, at the resolution of the event and 28 days following the event. A portion of the sample		

During Treatment Study Schedule

		Study Period	Study Treatment Period														
		Cycle/Visit	1				2				3-X						
		Duration	28 days				28 days				28 days						
		Relative Day within Dosing Cycle	1	2	3	8	15	22	1	8	15	22	1	8	15	22	
Procedure Category	Procedure																Comments
Lab/ Diagnostic Tests (cnt'd)	Proteomic blood sample	X	X			X			X		X		X				See Attachment 3 . Sample is only collected through Cycle 6.
	Stored sample for pharmacogenomics	X															Collect once. Sample can be collected at any time if not collected on C1D1.
	Exploratory biomarker blood sample	X											X				Sample to be collected C7D1.
	Central ECG	X	X	X	X	X	X	X	X	X	X	X	X	X*	X	X*	In Cycle 1, triplicate ECGs collected predose, at EOI, 2 hours EOI, and 6 hours EOI on the day of dosing . If possible, obtain prior to any associated blood draws. In Cycles 2-X, single ECGs should be obtained predose on the day of dosing. On non-dosing days,the ECG may be obtained anytime, but if possible they should be obtained near to the same time of day as the C1D1 ECG. See Attachment 4 . *Schedule 2 only
	Tumor markers								X				X				If applicable to tumor type of the patient; may be drawn up to 3 days prior to the planned assessment.
	Optional tumor biopsy															X	
Tumor Assessment	Tumor measurement (palpable or visible)											X			X		Perform at least every 8 weeks at the end of every even cycle.
	Radiologic imaging according to RECIST											X				X	The same method of imaging used at baseline should be used for each subsequent assessment. Perform at least every other cycle (approximately every 8 weeks). May be omitted if patient has clear signs of progressive disease.
Adverse Events Collection/CTCAE Grading					X						X				X		
Concomitant Medication Notation					X						X				X		
	LY3164530 – Schedule 1	X				X			X		X		X		X		

	LY3164530 – Schedule 2	X			X	X	X	X	X	X	X	X	X	X	
--	------------------------	---	--	--	---	---	---	---	---	---	---	---	---	---	--

^a Following discussion and agreement from the Sponsor, the frequency of some assessments may be reduced for patients that have been on treatment for more than 1 year and are continuing to derive benefit from treatment. This decision will be documented in writing.

Post-Treatment Discontinuation Schedule

Study Period	Post-discontinuation Follow-Up	
Visit 801		Post-treatment discontinuation follow-up should begin after the last dose of study therapy or, if study therapy has been omitted for an extended period, the date it is decided that the patient will not restart study therapy.
Duration	28 ±5 days	
Relative Day	28	

Procedure Category	Procedure		Comments
Physical Examination	Weight	X	
	Vital signs	X	Includes blood pressure, pulse, and temperature.
	ECOG performance status	X	
Tumor Assessment	Tumor measurement (palpable or visible)	X	Performed if lesion is assessed as target or non-target. Not required if progressive disease is documented while on treatment.
	Radiologic imaging according to RECIST	X	The same method of imaging used at baseline should be used for each subsequent assessment. Not required if progressive disease is documented while on treatment or if there are clear signs of clinical progression.
Adverse Events Collection/CTCAE Grading		X	After Visit 801, only study protocol- or drug-related events are reported. If a patient has an ongoing AE or SAE possibly related to LY3164530 (eg, abnormal electrolytes), the patient should be followed until the event is resolved, the event is no longer considered to be drug-related, the event becomes stable or returns to baseline, a new treatment is initiated for the patient, or the patient dies or is lost to follow-up. Any subsequent follow-up(s) for AEs will be no more than 28 days ±5 days in duration.
Concomitant Medication Notation		X	
	Local hematology	X	
	Local chemistry	X	Particular focus should be placed on patients that have abnormal electrolytes, as electrolyte depletion is known to occur for >6 weeks after EGFR monoclonal antibody therapy.
	Central ECG	X	Single ECG.
	Tumor markers	X	If applicable to tumor type of the patient.

Lab/ Diagnostic Tests	Optional tumor biopsy	X	From patients willing to consent.
	Exploratory biomarker blood sample	X	
	PK sample	X	
	Immunogenicity sample	X	In addition to the scheduled sample, if a patient should have an infusion reaction to LY3164530, all attempts should be made to obtain immunogenicity sample as close to the onset of the event as possible, at the resolution of the event, and 30 days following the event. If a patient requires subsequent follow-ups (eg, for an ongoing AE), an immunogenicity sample should be obtained, if possible. A portion of the sample taken for immunogenicity testing may be used for PK analysis.
	MET and EGFR ECD pharmacodynamic samples	X	
	MET and EGFR ligand pharmacodynamic samples	X	
	Proteomic blood sample	X	Only if patient discontinues prior to Cycle 6.

Abbreviations: AE = adverse event; BL = baseline; C = cycle; CT = computed tomography; CTCAE = Common Terminology Criteria for Adverse Events; D = day; ECD = extracellular domain; ECG = electrocardiogram; ECOG = Eastern Cooperative Oncology Group; eCRF = electronic case report form; EGFR = epidermal growth factor receptor; EOI = end of infusion; HPV = human papillomavirus; MET = mesenchymal-epithelial transition factor; MRI = magnetic resonance imaging; PK = pharmacokinetic; RECIST = Response Evaluation Criteria in Solid Tumors; SAE = serious adverse event.

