7.2.2. Dose Escalation

7.2.2.1. Dose-Limiting Toxicity Determination

Dose-limiting toxicity is defined as an AE during Cycle 1 that is considered by the investigator to be at least possibly related to LY3164530 and fulfills any one of the following criterion using the National Cancer Institute (NCI) Common Terminology Criteria for Adverse Events (CTCAE) v 4.03:

- \geq Grade 3 non-hematological toxicity. Exceptions will be made for:

- nausea, vomiting, diarrhea, and constipation that can be controlled with treatment. Grade 3 and Grade 4 nausea, vomiting, or diarrhea should be considered DLTs if persisting more than 48 hours despite supportive intervention.
 - Grade 3 rash that resolves with treatment to \leq Grade 1 within 14 days
 - Grade 3 or 4 asymptomatic electrolyte abnormalities that respond to standard treatment
 - Grade 3 elevations of ALT and/or AST lasting fewer than 8 days, without evidence of other hepatic injury, in the setting of preexisting hepatic metastasis and baseline elevation of these values, may not be considered a DLT if agreed by the study investigator and Lilly CRP/CRS.
- Grade 4 neutropenia or leukopenia, of >7 days duration.
 - Grade 4 thrombocytopenia of any duration.
 - Grade 3 thrombocytopenia with bleeding.
 - Any febrile neutropenia.
 - Any other significant toxicity deemed by the primary investigator and Lilly clinical research personnel to be dose limiting (eg, any toxicity that is possibly related to the study drug that requires the withdrawal of the patient from the study during Cycle 1).

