7.2.4.2. Skin Reactions

Skin rash is a known toxicity of EGFR inhibitors, and skin effects were observed with LY3164530 in a 5-week repeat-dose toxicity study in monkeys. In Study JNBA, skin reactions were observed at all dose levels with Schedule 1 and were dose limiting at 1250 mg. As a result, prophylaxis is permitted for the initial dose of LY3164530. Institutional-approved standard of care premedication for EGFR inhibitors, such as dexamethasone and/or topical and/or oral antibiotics, may be administered for the initial and subsequent doses.

Section 7.2.4.1 and Table JNBA.4 detail the treatment recommendations for LY3164530 skin reactions.

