8.1.2. Adverse Events

Lilly has standards for reporting AEs that are to be followed regardless of applicable regulatory requirements that may be less stringent. A clinical study AE is any untoward medical occurrence in a patient or clinical investigation subject administered a pharmaceutical product and which does not necessarily have a causal relationship with this treatment. An AE can therefore be any unfavorable and unintended sign (including an abnormal laboratory finding), symptom, or disease temporally associated with the use of medicinal (investigational) product whether or not related to the medicinal (investigational) product. Any clinically significant findings from labs, vital sign measurements, and so on that occur should also be reported to Lilly or its designee as

an AE. Lack of drug effect is not an AE in clinical studies because the purpose of the clinical study is to establish drug effect.

The investigator, monitor, and Sponsor will review the collected data regularly for evidence of AEs. All patients will be assessed routinely for AEs as outlined in the study schedule. All AEs observed will be graded using CTCAE v 4.03.

The CTCAE v 4.03 will serve as the reference document for choosing appropriate terminology for, and grading the severity of, all AEs and other symptoms. All AEs observed will be graded using CTCAE v 4.03. Any minor version of CTCAE v 4.0 (eg, v 4.03) may be used for this study. Minor CTCAE v 4.0 updates from the NCI will not necessitate a protocol amendment. For AEs without matching terminology within the CTCAE v 4.03 criteria, the investigator will be responsible for selecting the appropriate system organ class and assessing severity grade based on the intensity of the event. Note that both CTCAE term (actual or coded) and severity grade must be selected by study site personnel and collected on the eCRF. This collection is in addition to verbatim text used to describe the AE.

In addition to collecting the AE verbatim, the CTCAE term, and the CTCAE severity grade, AE verbatim text will also be mapped by the Sponsor or designee to corresponding terminology within the Medical Dictionary for Regulatory Activities (MedDRA) dictionary.

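### No on-drug skin inspection is scheduled in Cycle 1 until the Cycle 2 exam, so the 14-day rash rule for the known dose-limiting toxicity relies on AE grading at unfixed times

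*Protocol*

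**What the plan says.** In the During Treatment Study Schedule of Protocol Attachment 1, skin is examined under "Physical exam (including weight and skin inspections", marked on Day 1 of Cycles 1, 2 and 3 onward. The comment for that row reads "May be completed up to 7 days prior to the treatment infusion". No other on-treatment row names the skin.

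Protocol Section 7.2.2.1 counts a related non-hematological toxicity of Grade 3 or higher as a DLT. One exception is a "Grade 3 rash that resolves with treatment to" at most "Grade 1 within 14 days". The DLT is judged on AEs: "Dose-limiting toxicity is defined as an AE during Cycle 1 that is considered by the investigator" to be at least possibly related.

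Protocol Section 7.2.4.2 reports that "skin reactions were observed at all dose levels with Schedule 1 and were dose limiting at 1250 mg".

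On AE ascertainment, Protocol Section 8.1.2 says "All patients will be assessed routinely for AEs as outlined in the study schedule". In that schedule, "Adverse Events Collection/CTCAE Grading" is a row of its own with one entry for each cycle and no named days. Section 8.1.1 leaves the frequency of AE follow-up to the investigator, subject to Table JNBA.5, and that table sets no interval for the on-therapy period.

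SAP Section 6.13 words the rash exemption differently: resolution to Grade 2 or lower within 8 days.

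**The concern.** Skin reaction is the toxicity that the protocol names as dose limiting in this study. Whether a Grade 3 rash counts as a DLT depends on three dated facts: when it began, how severe it became, and when it fell to the exempting grade. The scheduled inspection interval is about twice the window in which those facts must be established. Blood counts and chemistry, which support other DLT criteria, have fixed Cycle 1 assessments on Days 8, 15 and 22. Rash has none.

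If some sites grade skin at each weekly visit and others rely on patient report, the same rash could be counted at one site and exempted at another. The DLT count feeds Figure JNBA.1 directly and, through it, the choice of RP2D.

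**Working it through.** The plan gives no figure on this point to reproduce. The check is a count of days.

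**Inputs**
- First on-drug skin inspection: day *e*. Cycle 2 Day 1 is Day 29 and the exam may be up to 7 days early, so *e* runs from 22 to 29 (Attachment 1).
- Window: 14 days (Section 7.2.2.1). The section does not say from when. I assume from onset of the Grade 3 rash on day *d*, and count an inspection on day *x* as inside the window if *d* < *x* ≤ *d* + 14.
- Possible onset days: 2 to 28, which is 27 days.
- Scheduled visits: Days 1, 2, 3, 8, 15, 22, 29, then Cycle 2 Day 8, which is Day 36 (Attachments 1 and 4, both schedules).

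**Step 1: interval between inspections.** Nominal: 29 − 1 = 28 days. Shortest: 22 − 1 = 21. Longest, with the Cycle 1 exam 7 days before first dose: 28 + 7 = 35.

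**Step 2: onset days with a dedicated inspection in the window.** These are days *e* − 14 to *e* − 1, which is 14 days, all lying within Days 2 to 28. The number uncovered is 27 − 14 = 13 for every *e*.
- *e* = 29: covered 15–28, uncovered 2–14 (13 days).
- *e* = 22: covered 8–21, uncovered 2–7 and 22–28 (6 + 7 = 13 days). The next exam is Cycle 3 Day 1 (29 + 28 = Day 57, or Day 50 if early), after the last window closes on 28 + 14 = Day 42.
- Onset on Days 2–7 is uncovered whatever *e* is. Counting Day 1 as a possible onset day gives 14 of 28.

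**Step 3: the same count for scheduled visits of any kind.**

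| Onset day | Visits within 14 days |
|---|---|
| 2 | 3, 8, 15 |
| 3–7 | 8, 15 |
| 8–14 | 15, 22 |
| 15–21 | 22, 29 |
| 22–28 | 29, 36 |

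Every onset day has at least two visits. The last falls 0 to 6 days before the window closes: onset on Day 8 closes on Day 22, a visit day; onset on Day 7 closes on Day 21, with the last visit on Day 15. Patient contact is adequate. What is missing is a stated requirement to inspect and grade the skin at that contact.

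**Step 4: effect of adding Days 8, 15 and 22.** With the Cycle 2 exam on Day 29, onset on Days 2–21 has two dedicated inspections in the window and onset on Days 22–28 has one. If the Cycle 2 exam is brought forward, onset from that day to Day 28 is again uncovered, unless the skin is also checked on Cycle 2 Day 1 itself.

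**Step 5: consequence of one reclassified rash in Figure JNBA.1.** 0/3 (E) becomes 1/3 (S); 1/3 (S) becomes 2/3 (D); 1/6 (E) becomes 2/6 (S). These show what one change does, not how often it would occur.

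**Step 6: the SAP's 8-day window.** The covered days are *e* − 8 to *e* − 1, which is 8 days, so 27 − 8 = 19 of 27 are uncovered.

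**The case against.** The strongest reply is that a DLT is never read from the physical-exam form. It is an investigator-judged AE with a CTCAE grade. AE collection and grading has its own row in every cycle, all on-therapy AEs must be reported (Section 8.1.2.2.2), and term and grade go on the eCRF (Section 8.1.2). A rash exempted because it resolved with treatment has, by definition, been seen and treated. After a known Grade 3 skin reaction, Table JNBA.4 holds dosing until Grade 1 or lower, which forces re-grading before the next infusion. All of this stands. A reader might infer that the rash rule cannot be applied from scheduled data; the documents do not support that.

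A reader might also infer that the gap is worse on weekly dosing, because 3 of 4 infusions per cycle on Schedule 2 have no scheduled skin inspection, against 1 of 2 on Schedule 1. That compares dosing visits. For the DLT rule, both schedules share the same exam days and visit days, so the 13 of 27 is the same on each.

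The reply does not supply fixed days. The AE row names none, Section 8.1.2 refers back to that row, and Section 8.1.1 leaves follow-up frequency to the investigator. Table JNBA.4 acts only once a Grade 3 reaction has been recognized, and it secures a grade before dosing rather than a dated recovery. On Schedule 1, Days 8 and 22 are not dosing days.

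**Conclusion.** The point holds as a gap in uniform ascertainment. Dedicated skin inspection misses the 14-day window for 13 of 27 possible Cycle 1 onset days, on both schedules and for any permitted date of the Cycle 2 exam. AE records can fill the gap, but nothing ensures that they do so on the same days at every site.

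The count assumes that the window starts at onset of the Grade 3 rash, and it gives onset days rather than probabilities. The documents do not give the distribution of rash onset or the chance of misclassification, so the effect on DLT counts cannot be estimated. The change is a cheap improvement; its absence does not invalidate the design.

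Separately, the protocol and SAP exemptions differ in both grade and duration. That difference can reclassify a rash however often skin is inspected, and the two passages must be reconciled.

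**What to change.** In Attachment 1, mark skin inspection with CTCAE rash grade at the existing Cycle 1 Day 8, 15 and 22 visits for both schedules. State that the dates of onset and of return to the exempting grade are recorded from these inspections plus any unscheduled assessments. So that late-onset rash is also covered, include a skin check on Cycle 2 Day 1 itself when that cycle's physical exam is done early.

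Inspections at later dosing visits are optional. Beyond the 14-day window of a Cycle 1 rash they inform only the review of DLT-equivalent toxicities, not the mTPI grid.

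Reconcile the rash exemption in Protocol Section 7.2.2.1 with that in SAP Section 6.13.

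The cost is a schedule-table amendment and a few minutes at visits that already take place, with no new visit or sample. With the inspections in place, recovery can be dated to within about a week.
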